#### **9.1.2. Handling of Withdrawals and Missing Data**

For the clinical outcome, patients with missing data or who are lost to follow-up will be considered as an indeterminate outcome and are included in the denominator for the calculation of clinical cure rate. Thus, patients with an indeterminate outcome are considered as failures for the analysis. A clinical failure occurring at an earlier time point will be carried forward to the subsequent visits.

In cases of missing or incomplete dates (e.g. AE and concomitant medications), the missing component(s) will be assumed as the most conservative value possible. For example, AEs with missing start dates, but with stop dates either overlapping into the treatment period or missing, will be counted as treatment-emergent, taking the worst-case approach. When partial dates are present in the data, both a partial start date and/or a partial stop date will be evaluated to determine whether it can be conclusively established that the AE started prior to the start of study drug or ended prior to the start of study drug. If the above cannot be conclusively established based on the partial and/or present dates, then the AE will be considered as treatment-emergent. Actual data values as they appear in the original eCRF will be presented in the data listings.

Missing values for other variables will not be imputed and only observed values will be used in data analyses and summaries.

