#### **6.4 Test of Cure Visit**

The TOC Visit will occur 7 days ( $\pm$ 2 days) after the EOT Visit.

The following procedures will be performed at the TOC Visit:

- Record concomitant medications;
- Perform a limited physical examination, if needed;
- Obtain vital signs, including blood pressure, heart rate, and respiratory rate, and, for ventilated patients, oxygen therapy and respiratory settings including FiO2 and PEEP;
- For patients with HABP, VABP, or VP, perform chest X-ray, MRI, or CT scan;
- Assess clinical signs and symptoms (see [Section 7.5](#));
- Assess clinical outcome. In Part A, clinical outcome will be assessed by the blinded assessor, in addition to the unblinded Investigator (see [Section 7.6](#));

Note: If a patient is a clinical failure at EOT, the patient is automatically considered a failure at the TOC Visit and LFU Visit, and the assessment of clinical response by the Investigator should be listed as “failure at EOT or TOC.”

- Collect blood samples for:
  - Serum chemistry;
  - Serum creatinine;
  - Hematology; and
  - Blood cultures in patients with bacteremia, if applicable;
- Collect urine sample for urinalysis;
- Collect infection site-specific cultures based on diagnosis if clinically indicated (see [Section 7.7](#)); and
- Assess adverse events.

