10. The Screening complete physical examination includes weight and height. A limited, symptom-based physical examination will be performed at the indicated visits. If a patient does not display symptoms, no limited physical examination needs to be performed.
11. Vital signs include blood pressure, heart rate, and respiratory rate, and, for ventilated patients, oxygen therapy and respiratory settings including FiO2 and PEEP.
12. For patients with HABP, VABP, or VP only. A chest X-ray, MRI, CT scan, or ultrasound done within 72 hours of Screening is acceptable. For images obtained >48 hours prior to randomization, repeat imaging is required. Note: If an ultrasound is performed, a confirmatory X-ray or CT scan must be performed within 24 hours. Findings should be consistent with the screening image and diagnosis of pneumonia, in the Investigator's judgment; otherwise, the patient is no longer eligible.
13. If a patient is a clinical failure at EOT, the patient is automatically considered a failure at the TOC and LFU Visits, and the assessment of clinical response by the Investigator should be listed as "failure at EOT or TOC."
14. In Part A, all clinical outcome assessments will be performed by a blinded assessor, in addition to the unblinded Investigator.
15. A respiratory specimen for BPP rapid diagnostic testing should only be collected for patients suspected to have HABP, VABP, or VP.
16. An APACHE II or SOFA score will be calculated at Screening and prior to randomization for patients in Part A only. For patients who are not being treated in an intensive care unit and cannot have an APACHE II or SOFA score performed, and for all patients in Part B, a qSOFA score should be calculated.
17. An APACHE II, SOFA, or qSOFA score that was calculated as standard of care within 24 hours of Screening may be used and does not need to be repeated at Screening.
18. Via IRT.
19. A highly sensitive urine or serum pregnancy test will be performed at Screening, EOT Visit, and ET Visit for women of childbearing potential.
20. Screening laboratories will be performed by the local laboratory within 48 hours of randomization. Subsequent laboratory samples will be collected, processed, and sent to the central laboratory for analysis.

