### **3.3.2. Blinded Assessor**

Study data will be collected and handled as if it were a blinded study.

For patients in Part A, each site will assign a blinded assessor, in addition to the unblinded Investigator, to evaluate criteria for clinical outcomes, conduct causality assessment for adverse events, and assess clinical signs and symptoms at study visits where an endpoint is evaluated. A blinded assessor must be qualified to perform medical evaluations and determine medical diagnoses (eg, physician, physician's assistant, or nurse practitioner [in the United States]). The blinded assessor may participate in the consenting process and Screening procedures, but once a patient is randomized the blinded assessor should have no other role in the study other than making blinded assessments. For consistency, whenever possible, the same blinded assessor should complete all blinded assessments for a study patient. All efforts will be made to keep the blinded assessor blinded during the course of the study. The blinded assessor should not have access to sections in the patient's medical record in which treatment group or dosing frequency are documented, should have no role in patient care or treatment, and should be restricted to limited sections of the patient's chart in order to assess clinical outcomes. Data collection by the blinded assessor will be used for entry into the electronic case report form (eCRF).

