#### **5.5. Efficacy Assessments**

##### **5.5.1. Clinical Outcome**

Clinical outcome will be used to determine a response of clinical success for all patients. Based on the assessment of signs and symptoms, the Investigator will choose 1 of the following clinical outcomes at the Day 5, Day 7, EOT, TOC, LFU and ET Visits, if applicable. In Part A, in addition to the unblinded Investigator, a blinded assessor will also determine clinical outcome. If there is a discrepancy between the assessment of the blinded assessor and unblinded Investigator, the assessment from the blinded assessor will be used. If there is a missing assessment from either the blinded assessor or unblinded Investigator, the other available assessment will be used. An adjudication committee may be organized for endpoint adjudication should it be deemed necessary by the DSMB. In such a case, a charter will be developed that describes their activities.

**Clinical cure:** complete resolution or significant improvement of signs and symptoms that were present at baseline and no new symptoms, such that no additional Gram negative antimicrobial therapy is warranted.

**Clinical failure:** symptoms present at study entry have not significantly improved or completely resolved, or new symptoms have developed and require the initiation of a non-study Gram negative antibacterial drug therapy, death, or intolerance to study drug leading to discontinuation from the study treatment.

**Clinical indeterminate:** determination cannot be made because of missing data or the patient is lost to follow-up.

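### SAP 9.1.2 carries a clinical failure forward from any earlier visit, which as worded includes Day 5 and Day 7; the visit notes in both documents state only failure at EOT as the trigger

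*SAP*

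**What the plan says.** The general rule is in SAP 9.1.2: "A clinical failure occurring at an earlier time point will be carried forward to the subsequent visits". The sentence lists no visits and has no condition that the later rating be missing.

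SAP 5.5.1 gives the visits at which there is a rating to carry: "the Investigator will choose 1 of the following clinical outcomes at the Day 5, Day 7, EOT, TOC, LFU and ET Visits". Day 5 and Day 7 are among them.

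Protocol 6.4 gives a specific trigger: "If a patient is a clinical failure at EOT, the patient is automatically considered a failure at the TOC Visit and LFU Visit". Protocol 6.5 repeats it. Appendix A note 13 has it as "If a patient is a clinical failure at EOT, the patient is automatically considered a failure at the TOC and LFU Visits", and note 13 to SAP Table 1 says the same. All four notes go on to tell the Investigator to record the response under a label that names TOC as well as EOT.

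Two further places help in reading the rule. For microbiologic persistence, SAP 5.5.2.1 does name its visits, from EOT to TOC. For clinical cure, SAP 5.2 lists EOT, TOC and LFU as endpoint visits, whereas Protocol 7.2 also lists Day 5 and Day 7.

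**The concern.** The SAP holds two carry-forward statements of different scope. A programmer who follows 9.1.2 literally lets a Day 5 failure override everything after it, including an observed cure at EOT. A programmer who follows note 13 starts carrying at EOT. The same patient can then be reported as a cure or as a failure, and the choice is left to programming.

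Clinical cure at TOC in the CRABC m-MITT Population is a listed secondary endpoint, and cure at EOT and LFU are secondary endpoints too. Presumed microbiologic outcomes (SAP 5.5.2) could follow if a carried-forward status counts as meeting the clinical criteria, which the SAP does not state. Site staff know the treatment assignment. If a blinded Day 5 rating is missing, the unblinded Investigator's rating stands in for it, so under 9.1.2 that rating could override a later blinded cure at TOC.

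**Working it through.** The plan gives no figure for this point, so the check compares the texts, asks whether the affected patient can exist, and then works out the size.

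**1. The two rules on one patient.** Take a patient rated failure at Day 5 who continues study drug and is rated cure from EOT onward.

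| Visit | Observed | SAP 9.1.2 as worded | Note 13 as worded |
|---|---|---|---|
| Day 5 | Failure | Failure | Failure |
| EOT | Cure | Failure | Cure |
| TOC | Cure | Failure | Cure |
| LFU | Cure | Failure | Cure |

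**2. All patterns.** With cure or failure at Day 5, Day 7, EOT, TOC and LFU (Day 7 distinct from EOT) there are 2^5 = 32 patterns.

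- The rules differ at TOC when there is a failure at Day 5 and/or Day 7 (3 ways), cure at EOT, cure at TOC and either rating at LFU: 3 × 2 = 6.
- They differ at LFU when EOT and LFU are cures and at least one of Day 5, Day 7 and TOC is a failure: 2^3 − 1 = 7. One of these is a failure at TOC only, with no Day 5 or Day 7 failure.
- Three patterns differ at both visits, so 6 + 7 − 3 = 10 of 32 differ at TOC or LFU.

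This counts logical combinations and says nothing about how often they occur.

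**3. Can the patient exist?**

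- Protocol 6.3 allows treatment up to 14 days and ties its end to clinical cure.
- The failure definition in SAP 5.5.1 begins: "symptoms present at study entry have not significantly improved or completely resolved, or new symptoms have developed and require the initiation of a non-study". If lack of improvement alone is enough, an unimproved Day 5 patient is a failure while still on study drug. If the need for a non-study drug qualifies both limbs, such a patient is much less likely to be rated failure. The text allows either reading.
- Indeterminate is not open to a patient who was seen, because it applies where "determination cannot be made because of missing data or the patient is lost to follow-up".
- In Part A, when the two raters disagree, "the assessment from the blinded assessor will be used". Under SAP 3.3.2 that assessor "should have no role in patient care or treatment", so a blinded failure rating does not by itself stop study drug.
- Against this, SAP 3.1 says a patient whose regimen must change for unsatisfactory response is classed as a failure and taken off study drug. Protocol 6.6 gives early stoppers a rated ET visit, and Protocol 6.3.7 lets Day 7 serve as EOT. For those patients the two rules normally agree.

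The patient is possible, at an unknown frequency.

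**4. Size per patient.** The effect on an arm's cure rate is 1/n.

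- CRABC m-MITT: 120 patients at 1:1 (SAP 4), so n = 60 and 1/60 = 1.7 points.
- m-MITT: about 200 enrolled in Part A, so n is at most about 100 and the effect is at least 1/100 = 1.0 point.
- Assumed counts of 0, 1, 3 or 6 patients in an arm of 60 give 0, 1.7, 5.0 or 10.0 points.

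**5. Effect on the difference.** SAP 9.3.2 uses a continuity-corrected interval. The half-width is 1.96 × √(p1(1−p1)/60 + p2(1−p2)/60) + 0.5 × (1/60 + 1/60).

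- Assumed 30/60 in each arm: 1.96 × √(0.25/60 + 0.25/60) + 0.0167 = 0.179 + 0.017 = 0.196. The difference is 0, 95% CI −19.6 to 19.6 points.
- Three more patients reclassified in one arm, 27/60 v 30/60: 1.96 × √(0.2475/60 + 0.25/60) + 0.0167 = 0.195. The difference is −5.0, 95% CI −24.5 to 14.5 points.

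If equal numbers are reclassified in arms of equal size, the difference does not move.

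**The case against.** The strongest reply is that there is no contradiction. The notes say that failure at EOT is enough to make TOC and LFU failures; none says that it is the only route. SAP 9.1.2 includes that case and extends it, as a pre-specified and conservative rule. This stands as far as it goes: the notes do not forbid carrying forward from an earlier visit. But the notes name a trigger that 9.1.2 makes redundant, and the two texts give different results for the patient in the table.

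The second reply is that the author probably meant only EOT to TOC to LFU. The SAP dropped the Day 5 and Day 7 cure endpoints, and the recording label in the notes, which names EOT and TOC, points to that sequence. This is plausible, and the fix adopts it. The SAP does not say it.

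The third reply is that the sentence sits under missing data and may only fill missing later visits. The sentence has no such limit. Missing outcomes already count as failures in the cure rate (SAP 9.1.2 and 9.3.2), so on this reading its main effect would be to keep a known failure with a missing TOC rating in the CE Population instead of losing that patient as indeterminate.

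The fourth reply is that the affected group is small by design. That may be so. Protocol 4.3, which mentions stopping drug and being a failure as an and/or, concerns staying enrolled and is weak evidence that failures continue treatment. The failure definition is itself ambiguous.

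**Conclusion.** The concern holds as an unresolved difference in scope between SAP 9.1.2 and the visit notes, and it should be settled before database lock. As worded, 9.1.2 turns an observed EOT, TOC or LFU cure into a failure for a patient rated failure on treatment who continues study drug and recovers.

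The number of such patients is unknown and may be zero. Each moves an arm's TOC cure rate by about 1.7 points in the CRABC m-MITT Population (60 per arm). The counts of 1, 3 and 6 and the 50% cure rate used above are assumptions. The illustrated 5-point shift in the difference is about a quarter of the CI half-width.

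A reader might infer three stronger things that the documents do not support:

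- That the SAP directly contradicts the protocol. The notes state a sufficient condition, not an exclusive one.
- That one arm is favoured. The documents give no Day 5 or Day 7 ratings, and the difference moves only if the arms are affected unequally.
- That the trial's conclusion is at risk. The primary endpoint is 28-day mortality, which this rule does not touch, and clinical cure has no margin or success rule.

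**What to change.** Align SAP 9.1.2 with note 13 by naming the visits, for example:

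> A clinical failure at EOT (including a Day 7 or ET visit serving as EOT) is carried forward to TOC and LFU, and a failure at TOC is carried forward to LFU. A Day 5 or Day 7 rating in a patient who continued study drug does not override an observed later rating.

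The TOC-to-LFU step goes beyond the trigger written in the notes but fits their recording label and 9.1.2. At TOC and LFU the new wording then departs from 9.1.2 only in the six patterns with a Day 5 and/or Day 7 failure followed by cure at EOT and TOC. No further imputation is needed, because missing ratings already count as failures in the cure rate.

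The cost is two sentences in the SAP before database lock and no new data. The downside is that the reported cure rate may be slightly less conservative. A table under any-visit carry-forward, with per-arm counts of reclassified patients, would show by how much; it is optional.

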#### **9.1.3. Baseline Definition**

For microbiological data, baseline pathogen(s) are determined from the specimens collected prior to the first dose of study drug.

For all efficacy and safety endpoints, baseline is defined as the last measurement or assessment prior to the first dose of study drug.

For safety endpoints, patients who were randomized into Part A then transferred into Part B will be included in both Part A and Part B, baseline is defined as the last measurement or assessment prior to the first dose of study drug of Part A for both Part A and Part B safety analysis.

For efficacy endpoints, patients who were randomized into Part A then transferred into Part B will be included in Part B only, baseline is defined as the last measurement or assessment prior to the first dose of study drug of Part A for Part B efficacy analysis.

## **9.2. Study Subjects**

### **9.2.1. Subject Disposition**

The number of patients randomized, treated, completed, and discontinued early from the study and the reasons for discontinuation will be summarized descriptively by treatment group for Part A and Part B in the ITT Population.

The following subject disposition categories will be included in the summary:

- Patients who were randomized,
- Patients who were randomized and treated,
- Patients who were randomized and not treated,
- Patients who completed the study treatment,
- Patients who did not complete the study treatment,
- Patients who did not complete the study treatment related to Coronavirus Disease 2019 (COVID-19);
- Patients who completed the study,
- Patients who did not complete the study, and
- Patients who did not complete the study related to COVID-19

For patients who did not complete the treatment, and patients who did not complete the study, a summary will be provided by reason of discontinuation. In addition, the number of patients in each analysis population and the reason(s) for exclusion from an analysis population (m-MITT, CRABC m-MITT, CE, ME, and CRABC ME) will be summarized by treatment group and a corresponding listing will be provided showing each patient's inclusion/exclusion from each population and reason(s) for exclusion.

### **9.2.2. Protocol Deviations**

The number of patients with at least one reportable protocol deviation, and the number of patients with at least one reportable deviation in each category will be presented by treatment group for Part A and Part B in the ITT Population. In addition, the protocol deviations related to COVID-19 will be categorized and summarized separately.

### 9.2.3. Demographic and Baseline Characteristics

Demographics and baseline characteristics including age (as a continuous variable and categorized as <65, 65-75 and >75 years), sex, race, ethnicity, weight, body mass index (BMI) (as a continuous variable and categorized as <25, 25-<30, 30-<35 and  $\geq$ 35), creatinine clearance (as a continuous variable and categorized as <15 mL/min, 15-<30 mL/min, 30-<60 mL/min, 60-<90 mL/min and  $\geq$ 90 mL/min), Charlson Comorbidity Index <3 or  $\geq$ 3, septic shock status at baseline, mechanical ventilation status at baseline, infection type (bacteremia, HABP, VABP, VP, cUTI, AP, surgical wound infection, and post-traumatic wound infection), APACHE II score [<10, 10 to 19, 20 to 30 and >30], SOFA score [<7, 7 to 9 and  $\geq$ 10], qSOFA score [<2, 2, 3 and >3], severity of illness (APACHE II [10-19]/SOFA [7-9]/qSOFA [2] and APACHE II [20-30]/SOFA [ $\geq$ 10]/qSOFA [3]) will be summarized by treatment group and baseline infection type (Overall, Bacteremia, HABP, VABP, VP, cUTI, AP, Surgical Wound Infection, and Post-traumatic Wound Infection) in the ITT, m-MITT, and CRABC m-MITT Populations. The demographics and baseline characteristics will be summarized for all regions and repeated for Mainland Chinese patients.

### 9.2.4. Baseline Pathogens

The pathogenic organisms identified from the baseline culture will be summarized by genus and species and regions (Overall, North America, Europe, Latin America, Asia-Pacific, and China) and by treatment group for the m-MITT, CRABC m-MITT, ME, and CRABC ME Populations. The number and percentage of patients with a monomicrobial ABC, polymicrobial ABC + other Gram-negative, or polymicrobial ABC + Gram-positive (with or without Gram-negative) infections will also be provided.

For the patients with cUTI or AP, the pathogen(s) cultured from urine at  $\geq 10^5$  CFU/mL or the same pathogen present in concurrent blood and urine cultures regardless of CFU values will be considered the baseline pathogen(s). If  $\geq 3$  bacterial isolates are identified from urine, the culture will be considered contaminated regardless of colony count unless 1 of the isolates that grows in the urine is also isolated from a blood culture.

For each treatment group, the MIC summary data (MIC50, MIC90, and MICrange and number of unique pathogens tested) for baseline pathogens will be summarized by region (Overall, North America, Europe, Latin America, Asia-Pacific, and China) and by treatment group in the m-MITT, CRABC m-MITT, ME, and CRABC ME Populations. The MIC50 and MIC90 will only be calculated for pathogens isolated from at least 10 patients within either treatment group.

The summary of susceptibility (susceptible and resistant) to ETX2514SUL and colistin for ABC baseline pathogen by region (Overall, North America, Europe, Latin America, Asia-Pacific, and China) will also be provided. For ABC baseline pathogens, ETX2514SUL susceptible is defined as MIC  $\leq$ 4 mg/L and ETX2514SUL resistant is defined as MIC >4 mg/L. For ABC baseline pathogens, colistin susceptible is defined as MIC <4 mg/L and colistin resistant is defined as MIC  $\geq$ 4 mg/L.

### 9.2.5. Medical and Surgical History

Medical and surgical history terms will be coded using MedDRA (Version 21.0). Medical and

surgical history will be summarized by treatment group and MedDRA system organ class (SOC) and preferred term in the Safety Population.

All Medical and surgical history will be listed by patient.

#### **9.2.6. Prior and Concomitant Medications**

Prior and concomitant medications will be coded using the World Health Organization (WHO) Drug Dictionary (Global B2 September 2018). Prior medications will include medications used before the first dose of study drug. Any medications used on or after the first dose of study drug will be included as concomitant medications.

The number and percentage of patients taking prior antibiotics within 14 days prior to the first dose of study drug and other prior medications within 14 days prior to the first dose of study drug will be summarized in the m-MITT, and CRABC m-MITT Populations by Anatomical Therapeutic Chemical (ATC) class and preferred term for each treatment group. In addition, the number and percentage of patients taking prior antibiotics within 72 hours prior to the first dose of study drug will be summarized in the m-MITT, and CRABC m-MITT Populations for each treatment group. The number and percentage of patients taking prior antibiotics within 24 hours prior to the first dose of study drug will also be summarized in the m-MITT, and CRABC m-MITT Populations for each treatment group.

The number and percentage of patients taking concomitant medications will be summarized in the same manner.

All prior and concomitant medications and procedures will be listed by patient.

